6.10.3. Secondary and Exploratory Efficacy Analyses

Key secondary efficacy measures will be tested in the order as specified in Section 6.4.

Table CGAX. 6.2 summarizes all the planned secondary and exploratory efficacy analyses for SP III, SP III/IV, and SP III/IV/V, not including analyses for health outcome measures. Additional statistical analysis details are also provided below.

Continuous Efficacy Measures

For the continuous secondary efficacy measures, the change from baseline will be estimated from MMRM as described for analysis for primary outcome or ANCOVA as described in Section 6.1.

For continuous secondary efficacy measures where the objective is to assess overall mean change during 3-month double-blind treatment phase, the endpoint for galcanezumab compared with placebo will be estimated as the treatment main effect from the MMRM analysis assessing the average treatment effect across Months 1, 2, and 3.

Binary Efficacy Measures

For the repeated binary efficacy measures such as responder indicators based on the number of migraine headache days, the visit-wise binary outcomes indicating whether patients meet X% response criteria will be analyzed using a categorical, pseudo-likelihood-based repeated measures analysis. This analysis will be implemented using the GLIMMIX procedure in SAS to compare treatments with covariates adjustment described in Section 6.2.

An unstructured covariance structure will be used to model the within-patient errors (denoted by TYPE=CHOL in the RANDOM statement). The Newton-Raphson method with ridging will be used for nonlinear optimization (denoted by including NLOPTIONS TECH=NRRIDG). The Kenward-Roger approximation will be used to estimate denominator degrees of freedom. If the model does not converge, the Fisher's scoring algorithm will be utilized by the SCORING option in SAS.

If the model still fails to converge, the model will be fit using covariance matrices in the following order specified by a decreasing number of covariance parameters until convergence is met:

- Heterogeneous Toeplitz,
- Heterogeneous autoregressive,
- Toeplitz, and
- Autoregressive.

If necessary, both fitting algorithms will be used in the pre-specified order before proceeding to the next covariance structure in the sequence.

For models where the unstructured covariance matrix is not utilized, the sandwich estimator (Diggle et al. 1994) will be used to estimate the standard errors of the fixed effects parameters. The sandwich estimator is utilized by the EMPIRICAL option in SAS. When the sandwich estimator is utilized, the Kenward-Roger approximation for denominator degrees of freedom cannot be used. Instead, the denominator degrees of freedom will be partitioned into between-subject and within-subject portions by the DDFM=BETWITHIN option in SAS.

For the binary secondary efficacy measures where the objective is to assess proportion of patients with X% response during the 3-month double-blind treatment phase, the endpoint for galcanezumab compared with placebo will be estimated as the treatment main effect from the categorical MMRM analysis assessing the average response rate across Month 1, Month 2, and Month 3.

For visit wise indicators of 50% responders, the results of the statistical tests at each month in the double-blinded treatment phase from categorical MMRM analysis will be used to assess the onset of 50% sustained response for galcanezumab compared with placebo. In particular, if the gated secondary measure of 50% response rate is statistically significant, then the earliest month where the statistically significant improvement is observed and maintained for all the subsequent months during double-blinded treatment phase will be considered as the period that demonstrated the onset of 50% sustained response.

For binary secondary efficacy measures such as the proportion of patients who maintain 50% response criteria for all 3 months of double-blind treatment, as well as the proportion of patients who demonstrate 50% response for all 3 months in the open-label treatment period among patients previously treated with galcanezumab who met 50% response criteria at Month 3 in the

double-blind treatment period, treatment differences will be determined using logistic regression with covariate of treatment, country and continuous baseline value.

Measures Conditional on the Postbaseline Number of Migraine Headache Days >0

The following measures are conditional on the number of migraine headache days >0:

- Mean severity of remaining migraine headaches

Those measures will be analyzed using MMRM model, assuming that data are missing for months without migraine headache.

The number of weekly migraine headache days in Month 1

If statistically significant improvement is observed at Month 1 and maintained for all the subsequent months during the double-blind treatment phase for the number of monthly migraine headache days, the number of weekly migraine headache days in Month 1 will be analyzed to identify the earliest week where the statistically significant improvement is observed and maintained for all the subsequent weeks in Month 1 for patients who have a monthly diary compliance rate greater than 50% for Month 1.

The number of weekly migraine headache days in Month 1 can be considered as ordinal data with possible values of 0, 1, 2, 3, 4, etc. and will be analyzed using an ordinal repeated measures model using the GLIMMIX procedure in SAS. In this model, a proportional odds model with cumulative logit link will be used, and a random intercept will be applied to the observations for each patient to account for repeated measures. The model will include the fixed, categorical effects of treatment, country, week, and treatment-by-week interaction, as well as the continuous, fixed covariate of weekly baseline number of migraine headache days and weekly baseline number of migraine headache days-by-week interaction. Log (number of compliant calendar days within each week/7) will be included as the offset in the model. For weekly diary compliance rate $\leq 50\%$, the number of weekly migraine headache days during that week will be considered missing.

The weekly baseline number of migraine headache days will be derived as (the monthly number of migraine headache days)/30*7.

Time to Event Measures

For the following time to event measures, a Kaplan-Meier curve of the time to event and treatment group comparison using stratified log-rank test stratifying for country, baseline MHD frequency category will be provided.

- Time to first 50% response in SP III for ITT population.
- Time to first loss of 50% response in SP V for patients who met 50% response criteria at their last injection interval and also entered SP V.

- Time to initiation of preventative treatment for migraine or probable migraine in SP V for patients who entered SP V and those who are not on concurrent preventive treatment group.

Distribution of Response Rate

Overall x% response rate during the double-blind treatment phase will be estimated for X=0, 5, 10, ..., 95, and 100, using GLIMMIX model as described earlier in this section. These estimated response rates will be plotted and points within each treatment group will be connected to show a curve of response rates. No statistical comparisons will be conducted among different treatment groups.

Analysis for PGI-I

When analyzing PGI-I, baseline PGI-S score will be included as a covariate. Specifically, it will be analyzed with an MMRM analysis while the covariates include the fixed categorical effects of treatment, month, country, baseline MHD frequency category and treatment-by-month interaction, as well as the continuous fixed covariates of baseline PGI-S score and baseline PGI-S score-by-month interaction.

Table CGAX. 6.2 Secondary and Exploratory Efficacy Variables and Analysis Methods

Efficacy Variables	SP III	SP IV, SP III/IV, SP III/IV/V, SP V
Number of migraine headache hours	MMRM	MMRM
Number of migraine attacks		
Number of days with acute medication use		
Number of headache days		
Number of moderate-severity headache days		
Number of headache hours		
Number of ICHD migraine headache days		
Mean severity of migraine headache		
Number of migraine headache days with nausea and/or vomiting		
Number of migraine headache days with photophobia and phonophobia		
Number of weekly migraine headache days in Month 1	GLIMMIX for ordinal outcome	N/A
X% response rate (X=30, 50, 75, or 100)	GLIMMIX	GLIMMIX
50% response sustained from month 1 to month 3	Logistic Regression	N/A
Proportion of patients maintained 50% response in SP IV among all galcanezumab-treated 50% responders at Month 3	N/A	Logistic regression
Time to first 50% response in SP III	Kaplan-Meier curve and stratified log-rank test	N/A
Time from the end of SP IV to no longer meeting 50% response criterion	N/A	Kaplan-Meier curve and stratified log-rank test for SP V
Time from the end of SP IV to start use of preventative treatment for migraine		
Distribution of response rate in SP III	GLIMMIX	N/A
Global Patient Impression – Severity	ANCOVA	MMRM

Abbreviations: ANCOVA = analysis of covariance; GLIMMIX = Generalized linear mixed model (for categorical variables); MMRM = Mixed models repeated measures; N/A= Not applicable.

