- **Time to first 50% response (in months)** is defined as the first month when 50% response is met. If a patient has not met 50% response during SP III, the patient will be censored at the last month of SP III where 50% response status is not missing.
- **Time to first loss of 50% response in post-treatment phase (in months)** is defined as the time from the beginning of the post-treatment phase to the first month when 50% response is no longer met during the post-treatment phase (SP V). If a patient has met 50% response during all the months of SP V, the patient will be censored at the last month where 50% response status is not missing. This analysis will be conducted only for patients who met 50% response criteria at their last injection interval and are also entered into SP V.

- **Time to initiation of treatment with a migraine preventive medication (in days) in the post-treatment phase** is defined as the disposition date of the previous study period before entering SP V to the date of start of the migraine preventive medication (based on information collected from concomitant medication electronic case report form [eCRF]) in the post-treatment phase. If a patient did not initiate preventive treatment during SP V, they will be censored at the disposition date of SP V. This analysis will be conducted only for patients who entered SP V and those who are not in concurrent preventive treatment group.
- **Number of migraine headache days with nausea and/or vomiting** is calculated as the total number of migraine headache days with an answer of “yes” to Question 10 “Yesterday, did you feel sick to the stomach or throw-up with the headache?” in a 30-day period.
- **Number of migraine headache days with photophobia and phonophobia** is calculated as the total number of migraine headache days with an answer of “yes” to Question Q9 “Yesterday, did the headache come with sensitivity to light and sound?” in a 30-day period.
- **Number of weekly migraine headache days in Month 1** is calculated as the number of migraine headache days in a 7-day period on which a migraine headache occurs. At month 1, the first 7 calendar days will be counted as week 1, the second 7 calendar days will be counted as week 2, the third 7 calendar days will be counted as week 3, and the rest of days will be counted as week 4.

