To assess the robustness of the MMRM results to deviations from normality assumption, a sensitivity analysis for raw number of migraine headache days (total number of migraine headache days for each interval without normalization to 30-day period) will be conducted with a repeated measures negative binomial regression model fitted with SAS PROC GLIMMIX. The model will include treatment, country, month, and treatment-by-month interaction, as well as the continuous fixed covariates of baseline number of monthly migraine headache days and baseline-by-month interaction, log (number of compliant days within each month/30) as the offset in the model. In case of non-convergence, country and/or baseline-by-month interaction may be excluded from the model. Directional consistency of treatment effects from this model and the primary analysis MMRM model as specified in Section 6.10.1 will be examined.

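### The weekly onset model uses a log-exposure offset on a cumulative-logit scale, where it does not correct for unrecorded diary days, and the response order that fixes its sign is not stated

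*SAP*

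**What the plan says.** If the Month 1 effect on monthly MHDs is significant and is maintained through Month 3, SAP 6.10.3 goes on to a weekly analysis intended to "identify the earliest week where the statistically significant improvement is observed and maintained for all the subsequent weeks in Month 1".

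- **Outcome.** The weekly counts "can be considered as ordinal data with possible values of 0, 1, 2, 3, 4, etc". The weekly derivation describes no rescaling to 7 days.
- **Model.** In GLIMMIX, "a proportional odds model with cumulative logit link will be used, and a random intercept will be applied" to each patient's observations. Fixed effects are treatment, country, week, treatment-by-week, weekly baseline and baseline-by-week.
- **Exposure.** "Log (number of compliant calendar days within each week/7) will be included as the offset in the model".
- **Sparse weeks.** At 50% weekly compliance or less, "the number of weekly migraine headache days during that week will be considered missing".
- **Week 4.** SAP 5.4.1.2 describes the weekly measure as a count over 7 days, but after three 7-day weeks "the rest of days will be counted as week 4".

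The SAP does not state whether P(Y<=j) or P(Y>=j) is modelled. A parallel offset appears in the negative binomial sensitivity model of SAP 6.10.2: "log (number of compliant days within each month/30) as the offset in the model".

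**The concern.** In a log-link count model, an offset of log(days) makes the expected count proportional to the days observed. That is the usual reading of the 6.10.2 model. On a cumulative logit, a coefficient of 1 on log(days) has no such meaning. Because the weekly counts are not rescaled, the offset is the only protection against unequal recording.

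If one arm records fewer days, it shows fewer MHDs without any drug effect. An offset that under-corrects leaves part of that artefact in the treatment contrast, and one with the wrong sign enlarges it. At stake is the week named as the onset of effect: a false early onset if the galcanezumab arm records less, or a missed real onset if the placebo arm records less.

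**Working it through.** **The plan's own figure.** The weekly analysis has none. The only design figure is about 90% power with 243 per arm, effect size 0.33, two-sided 0.05 and 20% discontinuation (SAP 5.2). With 243 × 0.8 = 194.4 per arm, the noncentrality is 0.33 × √(194.4/2) = 3.25 and t-test power is 0.901. It reproduces, but does not bear on this point.

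**Size of the offset.** Inputs are 4 to 14 MHDs per 30 days (SAP Table CGAX. 5.1) and m = 4 to 7 recorded days in a 7-day week (from the 50% rule). I assume independent days, so Y ~ Binomial(m, p) with p = MHDs/30.

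- Offset supplied: log(m/7), which is -0.154, -0.336 and -0.560 for m = 6, 5 and 4.
- Shift needed: logit P(Y>=j | m) − logit P(Y>=j | 7).
- Coefficient needed: shift needed ÷ log(m/7).

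At 8 MHDs (p = 0.267) with m = 5 (offset -0.336):

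| Cut-point | P, 7 days | P, 5 days | Shift needed | Coefficient needed |
|---|---|---|---|---|
| Y>=1 | 0.886 | 0.788 | -0.738 | 2.19 |
| Y>=2 | 0.596 | 0.402 | -0.783 | 2.33 |
| Y>=3 | 0.279 | 0.122 | -1.025 | 3.05 |

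Over m = 4 to 6 and j = 1 to 3, the coefficient needed is 1.4 to 3.4 at 4 MHDs and 3.2 to 4.2 at 14 MHDs. No single fixed value fits all cut-points.

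**Sign.** Fewer recorded days give a negative offset. Added to logit P(Y>=j), it predicts fewer MHDs: the right direction, but too small. Added to logit P(Y<=j), it predicts more MHDs: the wrong direction.

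**Effect on the onset week.** I simulated 800 trials per scenario with 243 per arm, four weeks, and the random-intercept cumulative logit with treatment-by-week and baseline-by-week terms. The comparator was a log-link Poisson model with the same offset and robust standard errors, fitted week by week. Assumptions: no effect in week 1; rate ratio 0.75 in weeks 2 to 4; completion gap in week 1 only, then 95%; days missing at random; 9-day week 4; mean on-study rate 78% of baseline.

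Chance that week 1 is significant in favour of galcanezumab (nominal 2.5%):

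| Completion, placebo vs galcanezumab | Offset on P(Y<=j) | Offset on P(Y>=j) | No offset | Log-link count |
|---|---|---|---|---|
| 95% vs 95% | 2.8% | 2.8% | 2.8% | 3.3% |
| 95% vs 92% | 7.4% | 4.8% | 6.0% | 2.8% |
| 95% vs 90% | 13.1% | 5.6% | 9.6% | 3.5% |
| 95% vs 85% | 35.7% | 10.2% | 21.5% | 2.2% |
| 90% vs 80% | 30.1% | 7.9% | 16.9% | 2.9% |

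Under the full maintained-to-the-end rule at 95% vs 85%, week 1 is named as onset in 32.5%, 9.9%, 20.5% and 2.2% of trials. Mean log-odds bias there is -0.32 on P(Y<=j) and -0.13 on P(Y>=j), against a standard error of about 0.20.

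With the opposite imbalance (85% placebo, 95% galcanezumab) and a true rate ratio of 0.75 in every week, week 1 is detected in 43%, 81%, 64% and 93% of trials, in the same column order.

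Monte Carlo standard error is about 0.6 points near 2.5% and 1.7 points near 35%. Simplifications: maximum likelihood by quadrature instead of pseudo-likelihood, country omitted, counts of 6 or more pooled, and the Month 1 trigger and monthly compliance filter not applied.

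**Week 4.** Visit 5 falls 30 ± 2 days after Visit 3 (Protocol, Schedule of Activities), so Month 1 is 28 to 32 days and week 4 is 28 − 21 = 7 to 32 − 21 = 11 days. The offset then ranges from 0 to log(11/7) = 0.45. A length common to all patients, such as log(9/7) = 0.25, is absorbed by the categorical week effect.

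**The case against.** The strongest reply is that the harm needs unequal completion between arms, and nothing in the documents points to it. The trial is double-blind, missed days can be entered at the next log-in (SAP Table CGAX. 5.2), entry requires at least 80% baseline completion (Protocol 6.1), and compliance is summarised by arm (SAP 6.8), so a gap would be visible. The analysis is also outside the gatekeeping sequence of SAP 6.4 and runs only after Month 1 onset is shown. All of this stands and limits the consequence. It does not rescue the offset, whose only purpose is to handle unequal exposure.

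Three stronger readings are tempting, and the documents do not support them.

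- *The offset definitely has the wrong sign.* The SAP does not state the response order, and a software default is not part of the plan.
- *The offset is worse than none.* That holds only for P(Y<=j). With P(Y>=j) it roughly halves the error at 95% vs 85% (10.2% against 21.5%).
- *The longer week 4 adds bias.* A common length cannot move the within-week treatment contrast. Only differences in week length or completion between arms could, and none is shown. What remains is the inconsistent description of the week.

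**Conclusion.** The point holds, as a minor one. The fixed coefficient of 1 is wrong under either response order: about 1.4 to 4.2 is needed on logit P(Y>=j), varying with cut-point and migraine rate, if days are independent. The unstated order decides whether the offset harms or under-corrects.

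The effect on the onset week depends on assumed completion rates. It is nil with equal completion, modest at a 3-point gap (7.4% or 4.8% against 2.5%) and large at a 10-point gap (about 30 to 36%, or 8 to 10%). The bias favours the arm that records less, so it can create or hide an early onset. The weekly onset statement is the only result exposed; the primary and key secondary tests do not use this model.

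**What to change.** Use a model in which exposure enters correctly. Either of these would do:

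- a repeated-measures count model with a log link and offset log(compliant days/7), adapted from SAP 6.10.2, with a fallback for non-convergence as that section has;
- a binomial model of MHDs out of compliant days, which also respects that the count cannot exceed the days recorded.

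The simulation supports handling exposure through a log link. It did not test the repeated-measures negative binomial itself.

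If the ordinal model is kept, drop the offset, enter recorded days as a covariate with an estimated coefficient, and state the response order. Separately, reconcile the 7-day definition in SAP 5.4.1.2 with the open-ended week 4.

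The cost is SAP wording and programming, with no new data. SAP 6.1 allows changes to the SAP only before unblinding; after that, the corrected model could be reported as an additional exploratory analysis and labelled as such.

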**To avoid biased reporting, patients must not be told the number of MHDs on which study qualification is based.**

**Study Period III:** At the start of the 3-month double-blind treatment phase (Visit 3), patients meeting all eligibility requirements will be randomized in a 1:1 ratio to receive placebo or 120-mg/month galcanezumab, respectively.

Patients randomized to the 120-mg dose of galcanezumab will receive an initial loading dose of 240 mg (2 injections of 120 mg each at Visit 3 only). To preserve blinding at Visit 3, each patient in any treatment groups will receive 2 injections of investigational product (2 placebo injections or two 120-mg galcanezumab injections).

The patient will be considered enrolled in the study when randomization occurs. During this phase, study procedures at dosing visits must always occur prior to the patient receiving their assigned treatment.

Patients will be given injections of investigational product during office visits ([Figure CGAX.1](#)). For all treatment groups, subcutaneous injections will be administered once monthly at the dosing visits. At Visit 3 (first dose), patients will be required to remain in the office for observation for 30 minutes post injection. Patients will continue to log in and complete the ePRO diary each day. Patients may continue to take their allowed acute migraine or headache medication (with some limitations; see [Section 7.7](#)) during the treatment phase and keep recording headache medication log.

Visit 4 (Month 0.5) will be a virtual visit through telephone by site staff and is to include a review of any spontaneously reported AEs, queries on concomitant medications, and performance of ePRO diary entries since last visit.

Patients will receive their last double-blind dose of investigational product at Visit 6 (Month 2). Patients who do not opt to continue into Study Period IV will receive no further injections and will proceed directly to the post-treatment follow-up phase.

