**Study Period IV:** Patients who complete the double-blind period of this study can opt to enter an open-label period (Study Period IV) for up to 3 months of treatment with 120-mg/month galcanezumab. Following completion of the double-blind period Visit 7 (Month 3) assessments and procedures, patients may enroll in the open-label period of the study and receive open-label study drug. Sites and patients will remain blinded to patients' previous treatment assignments. To preserve blinding at Visit 7, each patient in any treatment group will receive 2 injections: patients randomized to placebo will receive an initial loading dose of 240-mg galcanezumab (2 injections of 120-mg galcanezumab at Visit 7 only); patients randomized to galcanezumab will continue the dose of 120 mg but also receive 2 injections (1 placebo injection and 1 120-mg galcanezumab injection at Visit 7 only). All patients will remain at the office for a 30-minute post-injection observation at this visit. At Visit 8 and Visit 9, all patients will receive a dose of 120-mg galcanezumab. Patients will continue to have efficacy and safety assessed, including daily completion of the ePRO diary and headache medication log (see Section 2, Schedule of Activities). Patients may continue to take their allowed acute migraine or headache medication as in Study Period III.

**Study Period V:** Patients who complete open-label treatment phase or discontinue for any reason during Study Period III or IV must enter into Study Period V for assessment during washout of investigational study drug. During this 4-month phase, sites and patients will remain blinded to patients' treatment assignments. Patients will follow all study procedures during Study Period V but will not receive galcanezumab or placebo. After completion of Visit 10 (Month 6) assessments, if clinically warranted due to a worsening of symptoms, patients may start migraine prevention medications at the discretion of the investigator. The list of allowed preventive medications will be provided separately. At Visit 12 (Month 10), patients will return to the site for their last study visit and be discharged from the study.

Visit 11 (Month 8) will be a virtual visit through telephone by site staff and is to include a review of any spontaneously reported AEs, queries on concomitant medications, and ePRO diary entries since last visit.

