## 5.4. Scientific Rationale for Study Design

The length of the randomized treatment phase is considered sufficient to assess the safety and efficacy of a migraine prevention medication, given the mechanism and observed onset of action for CGRP antibodies as well as the evidence of efficacy and safety from completed Phase 2 and Phase 3 studies of galcanezumab and from other drugs in the same class (Dodick et al. 2014a,

2014b; Goadsby et al. 2017; Skljarevski et al. 2018). A 3-month open-label phase is included to enlarge study drug exposure. A 4-month post-treatment follow-up phase is included to evaluate patient safety during wash-out of galcanezumab. This allows for a total of 5 months of observation from the time of last injection of galcanezumab. A 5-month post-treatment observation period allows for a wash-out of approximately 5 elimination half-lives of galcanezumab and should decrease galcanezumab serum concentrations by approximately 97% during this time.

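### The SP V log-rank tests leave their treatment groups undefined after crossover, and the placebo-arm curve would mix galcanezumab-exposed with placebo-only patients

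*SAP*

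**What the plan says.** SAP 6.10.3 (Time to Event Measures) plans a Kaplan-Meier curve and a "treatment group comparison using stratified log-rank test" for three endpoints, two of them in SP V: first loss of 50% response and start of preventive treatment. The strata are country and baseline migraine frequency. The loss-of-response set is everyone with a 50% response in the final injection interval who entered SP V. Neither SP V endpoint requires that the patient ever received galcanezumab.

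Patients reach SP V by several routes. Under Protocol 5.1, completers who decline the open-label period "will proceed directly to the post-treatment follow-up phase", and those who "discontinue for any reason during Study Period III or IV must enter into Study Period V". Placebo patients who do enter SP IV receive galcanezumab at Visits 7, 8 and 9, beginning with 240 mg.

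On the start of the clock, SAP 5.4.1.2 has loss of response "defined as the time from the beginning of the post-treatment phase to the first month when 50% response is no longer met". It times preventive start from the disposition date of whichever period preceded SP V. Table CGAX. 6.2 labels the same two endpoints "Time from the end of SP IV to no longer meeting 50% response criterion" and "Time from the end of SP IV to start use of preventative treatment for migraine".

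Both endpoints are tertiary (SAP 4) and outside the testing hierarchy (SAP 6.4).

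**The concern.** A between-group test in SP V needs groups that mean something in SP V. The SAP defines only two, the randomized arms, and analyses the ITT population by randomized assignment. Its post-treatment population is given no grouping rule. Randomized arm is therefore the natural reading, though not a stated one. On that reading the two groups have mostly both been on galcanezumab, for different lengths of time. For loss of response they are also selected on a post-randomization outcome, so randomization no longer protects the comparison. Placebo-only patients contribute to the placebo curve although they have no galcanezumab effect to lose.

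What is at stake is interpretation. A p-value tabulated as galcanezumab versus placebo during washout invites a placebo-controlled withdrawal claim that the design cannot support.

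**Working it through.** **The plan's own figure.** The documents give no sample size, event count or power for SP V. The inputs used here, 243 per arm and 20% discontinuation, come from Protocol 10.1 and SAP 5.2, and they reproduce. A two-sided 0.05 t-test with 90% power and effect size 0.33 needs 193.94, so 194 per arm and 388 evaluable. Then 194/0.80 = 242.5, so 243 per arm and 486 in total.

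**Who enters SP V.** Setting Protocol 5.1 against the dosing visits gives four sequences:

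| Randomized arm | Entered SP IV? | Galcanezumab dosing visits before SP V |
|---|---|---|
| Galcanezumab | Yes | up to 6 |
| Galcanezumab | No | up to 3 |
| Placebo | Yes | up to 3, the first 240 mg |
| Placebo | No | none |

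Apart from dosing errors, the galcanezumab arm contains only exposed patients, because ITT membership requires at least one dose.

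**Never-exposed placebo patients.** Let q be the proportion of placebo completers who decline SP IV. The documents do not give q, so it is assumed. If everyone enters SP V:

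never exposed = 243 × (0.20 + 0.80q)

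| q (assumed) | Never exposed | Share of placebo arm |
|---|---|---|
| 0% | 48.6 | 20% |
| 10% | 68.0 | 28% |
| 20% | 87.5 | 36% |
| 30% | 106.9 | 44% |

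Preventive start has no responder filter, so these shares carry over to it if retention into SP V is equal.

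**Share of the loss-of-response set.** With n0 never-exposed and n1 exposed placebo-arm patients, and last-interval response rates r0 and r1 (also assumed):

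share = n0·r0 / (n0·r0 + n1·r1)

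- Low: q = 0, r0 = 10%, r1 = 60%. 48.6 × 0.10 = 4.9 and 194.4 × 0.60 = 116.6, so 4.9/121.5 = 4%.
- High: q = 20%, r0 = 40%, r1 = 60%. 87.5 × 0.40 = 35.0 and 155.5 × 0.60 = 93.3, so 35.0/128.3 = 27%.
- If both rates were 50% with q = 20%, the share would be 36%.

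In the 4-27% range, 73-96% of the placebo-arm risk set had been on galcanezumab.

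**Time origin.** Someone going from SP III to SP V has no end-of-SP-IV date. That person does have an SP V start and an SP III disposition date, which are the two origins SAP 5.4.1.2 uses. The definitions work for every entrant; the two table labels contradict them.

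**Practice elsewhere in the documents.** SAP 6.1 analyses the open-label population as one group because all start on the same treatment. Protocol 10.3.4.1 restricts categorical safety comparisons in SP IV and SP V to description. The SP IV maintenance endpoint is limited to patients previously given galcanezumab (SAP 5.4.1.2), and SAP 6.1 defines a galcanezumab-treated population. None of these rules is carried to the SP V endpoints.

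**The case against.** The sponsor can fairly say that these are tertiary endpoints, that the SP V objective is to assess change and not to compare with placebo, and that the follow-up phase exists "to evaluate patient safety during wash-out of galcanezumab". All of that is true and limits the importance of the point. It does not explain why a between-group log-rank test is planned.

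The size is also open to challenge. The 20% is a sample-size allowance. Some of those patients will leave the study altogether. The post-treatment population requires an SP V visit. Early discontinuers can have a missing last-month response under the diary-compliance rule in SAP 5.4.1.1. So 49 is a ceiling for the discontinuation route at the planned rate, and the percentage shares rest on assumed response and opt-out rates. This stands.

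Three stronger readings are tempting, and the documents do not support them:

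- That patients who skip SP IV have no time origin. SAP 5.4.1.2 gives them one.
- That the SP V analyses cannot describe loss of effect after galcanezumab. The galcanezumab-arm curve does so; the problem lies in the placebo-arm curve and the contrast.
- That the log-rank result will be flat. Nothing in the documents allows that prediction.

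**Conclusion.** The point holds in limited form. The SAP plans a treatment-group log-rank test for two SP V endpoints without defining the groups. Read as randomized arms, an inference but the natural one, the test mostly contrasts longer with shorter prior galcanezumab exposure, and the placebo-arm curve is a mixture. Never-exposed patients number at most about 49 of 243 through the planned discontinuation, plus an unknown number of SP IV decliners. The 4-27% share of the loss-of-response set illustrates the scale and is not an estimate from the documents. The time-origin defect is a contradiction between labels and definitions, not a missing definition. The endpoints are tertiary and outside gatekeeping, so no primary, key secondary or safety conclusion changes. The change is still worth making, because these are two of the three SP V efficacy endpoints listed in SAP 4.

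**What to change.** In SAP 5.4.1.2, 6.10.3 and Table CGAX. 6.2:

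- Restrict the main loss-of-response curve to responders whose last injection was galcanezumab.
- Define the SP V groups by actual treatment sequence, and show placebo-only patients separately and descriptively.
- Drop the log-rank test by randomized arm, or relabel it as a descriptive comparison of longer with shorter prior galcanezumab exposure.
- Correct the two Table CGAX. 6.2 labels to match SAP 5.4.1.2, keeping its origins: start of SP V for loss of response, and disposition date of the preceding period for preventive start.

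The cost is wording and table shells. The sequences can be derived from the dosing records described in SAP 6.14.1. One tertiary p-value is lost, and the placebo-only group will be small. SAP 6.1 allows SAP changes only before unblinding; after that, the change and its justification belong in the clinical study report.
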